## III. APPROACH

We propose a two-center, randomized, double blind, placebo-controlled, parallel, three-episode, clinical trial of rizatriptan 10 mg oral tablets versus placebo for treating spontaneous vestibular attacks in patients with VM.

Our primary Specific Aim is to test hypotheses 1a-1d that rizatriptan will be:

- 1a. Superior to placebo in reducing the severity and duration of vestibular attacks as measured by:
  - (1) Proportion of treated attacks in which subjects experience a reduction in severity rating from Grade 3/2 to Grade 1/0 at one hour after taking study medication (see below for rating description). This is the main outcome measure; 1a(2)-1d(2) are secondary outcome measures.
  - (2) Proportion of treated attacks in which subjects achieve sustained relief (i.e., vestibular symptom severity rating of Grade 1/0) for 24 hours after taking study medication, without use of non-study therapies.
  - (3) Proportion of treated attacks in which subjects experience freedom from vestibular symptoms (i.e., severity rating of Grade 0) at one hour after taking study medication.
  - (4) Use of fewer non-study therapies after each attack treated with study medication.
- 1b. Superior to placebo in reducing severity of symptoms associated with vestibular attacks as measured by:
  - (1) Proportion of treated attacks in which subjects experience relief (reduction to Grade 1/0) from VM-associated symptoms (e.g., nausea, vomiting, motion sensitivity, gait disturbance, headache, photophobia, and phonophobia) at one hour after taking study medication.
  - (2) Proportion of treated attacks in which subjects achieve sustained relief from VM-associated symptoms for 24 hours after taking study medication without use of non-study therapies.
- 1c. Superior to placebo on treatment satisfaction and health-related quality of life as measured by:
  - (1) Scores on the Treatment Satisfaction Questionnaire for Medication (TSQM) at 48 hours after each attack treated with study medication
  - (2) Scores on the Short Form 12 (SF-12) at 48 hours after each attack treated with study medication
- 1d. Tolerated as well as placebo by patients with VM as measured by:
  - (1) No greater rate of treatment-emergent serious adverse events reported on the NCI Common Toxicity Criteria Scale 4.0^59 obtained 48 hours after each attack treated with study medication.

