  - (2) No greater rate of treatment discontinuation for adverse events of any type or severity.

Our secondary Specific Aim is to gather data that will be needed to establish rigorous inclusion and exclusion criteria, determine sample sizes, and prepare Manuals of Operating Procedures for future Phase III treatment trials of rizatriptan and other abortive and prophylactic medications for VM. We intend to gather the following specific information during the Observation Phase of this study, which will last up to 12 months:

- 2a. The natural range of frequency and severity of vestibular attacks in treatment-seeking patients with VM.

Our goal is to identify the mean, median, and range of naturally occurring vestibular attacks in patients with VM, allowing future investigators to accurately estimate the sample sizes and study durations needed for abortive and prophylactic medication trials.

2b. The type and severity of medical and psychiatric conditions that commonly coexist with VM. Our goal is to identify the prevalence and severity of common comorbidities of VM, allowing future investigators to make informed decisions about the inherent compromise between excluding subjects with potential confounds versus including subjects with manageable comorbidities to maintain real world generalizability.

2c. The types, doses, and frequency of use of prescription and non-prescription medications for VM. Our goal is to create a compendium of usual clinical care and self-treatment of VM, giving future investigators naturalistic data to (1) guide selection of allowable co-treatments in future studies of prophylactic and abortive medications for VM and (2) determine which usual care treatments may be worthy of future controlled trials.

We also intend to collect the data described in 2a-c through the treatment phase of the study. Our goal is to conduct exploratory analyses of the influence of these variables on the efficacy of rizatriptan for VM, further enhancing the design of future Phase III trials and providing possible insights into the pathophysiology of VM

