## **J. Statistical Methods**

**1. Power Analysis.** The primary goal of this Phase II study is to demonstrate sufficient superiority of rizatriptan over placebo in the main outcome measure, 1a(1), to warrant a future Phase III trial. In the previous triptan study for VM (see Prior Controlled Study of Triptans for VM), the response rate for active drug was 3/8 (38%) versus 2/9 (22%) for placebo. If the small sample from that failed trial reflected a true response, then the odds ratio favoring the triptan for VM would be 2.1. To improve our estimate, we examined the results of two large registration trials that used a simple randomization design similar to the present proposal to test rizatriptan for conventional migraine. Those studies had response rates of 74% and 77% for rizatriptan versus 28% and 37% for placebo giving odds ratios of 7.4 and 5.7 favoring rizatriptan. The lower response rates in the VM trial most likely reflected the inadequate sample size, but could suggest that triptans are less effective for VM than conventional migraine. To account for this possibility, we took the limited results of Neuhauser, et al. as a worst-case scenario for our sample size calculation. Focusing on the main outcome measure, 1a(1), in this double-blind, randomized trial, with PASS simple randomization design and using a type I error of 0.05, type II error of 0.2 (equivalent to power of 80%), two-sided tests, then treating 120 subjects (with 2:1 ratio for treatment and placebo) will allow us to detect an odds ratio as small as 3.2. Thus, the plan to enroll 200 subjects in the Observation Phase and select 120 for the Treatment Phase will be sufficient, even if the response of VM to rizatriptan proves to be only half that of conventional migraine. Phase II trials typically gather data on secondary outcomes (e.g., 1a(2)-1d(2)) and other variables (2a-c) to inform the design of Phase III trials, but sample sizes need not be planned to demonstrate significant differences in these variables.

**2. Randomization.** A randomization scheme will be developed to assign the 120 patients expected to be included in the Treatment Phase to parallel treatment arms in a 2:1 ratio of active drug:placebo.

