**3. Statistical Analysis and Modeling.** We will use SAS and R^70 statistical software, creating ad hoc algorithms and macro procedures to solve analytical questions for which no marketed algorithms exist.

1. As a first step to understanding the nature of our data, we will conduct univariate analysis of demographics, primary and secondary outcome measures, illness-related variables (e.g., frequency, severity, and duration of vertigo attacks), associated symptoms, comorbid conditions, and self-report rating scales. The marginal distribution of each measure will be calculated at each time point and across time. The time trends of outcome measures will be evaluated by graphical analyses. For example, parallel plots for each of the outcome measures will be created to examine the patterns of change over time.

2. We will test the four hypotheses of Specific Aim #1 using bivariate methods and multivariate modeling. First, we will analyze differences between rizatriptan and placebo on all outcome measures at each time point using chi-squares to cross-tabulate categorical variables, and t-tests, analyses of variance (ANOVAs), or marginal regressions to compare continuous variables.

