4. We will use this 3-step analysis procedure to test all outcome measures for hypotheses 1a-1d. However, the principal result of the study will be determined by the findings of bivariate analyses and multivariate modeling of the main outcome measure, 1.a.(1), plus favorable findings on tolerability measures, 1d(1)-1d(2). We will include all subjects who treat at least one vertigo attack with study drug (i.e., intent-to-treat analysis). A statistically significant result favoring rizatriptan over placebo on 1a(1) and absence of statistically significant differences on 1d(1)-1d(2) will support development of a Phase III clinical trial of rizatriptan for treating vestibular attacks in patients with VM. The design of future trials will also be informed by results of tests of secondary measures 1a(2)-1c(2). We did not hypothesize equal tolerability for rizatriptan and placebo, but rather an absence of significantly higher rates of serious adverse effects and drug-related treatment discontinuation, so our statistical analyses of measures 1d(1)-1d(2) will not include equivalence tests.

[figure not shown]

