7. Interim analysis: We will conduct an interim analysis at study midpoint without breaking the blind to assess (1) recruitment, (2) safety, and (3) efficacy. Plans for shortfalls in recruitment are noted below. We will terminate the study for insufficient safety if there is a statistically significant difference between arms in adverse events of greater than minor severity, or for lack of efficacy if response rates are <25% in both arms, i.e., no better than placebo rates in previous triptan trials. We will continue the study if the primary outcome, 1(a)1, is >25% in at least one arm, but not statistically different between arms. If the primary outcome is statistically different, then we will terminate the study because the primary aim will be met. We will break the blind and identify the results as positive (rizatriptan superior to placebo) or negative (rizatriptan inferior to placebo).

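### The Phase III go statement counts a non-significant test on two unpowered tolerability measures as a favourable finding, which cannot support hypothesis 1d as worded

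*Combined protocol and SAP*

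**What the plan says.** All places are in the combined protocol and SAP.

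- **Hypothesis 1d (III. Approach)** is that rizatriptan will be "Tolerated as well as placebo by patients with VM as measured by" two measures. The first is a rate of treatment-emergent serious adverse events no greater than on placebo. The second is "No greater rate of treatment discontinuation for adverse events of any type or severity".
- **Power Analysis (III.J.1)** sizes the trial on 1a(1) alone: 120 treated subjects at 2:1, two-sided 0.05, 80% power, odds ratio 3.2. For the secondary outcomes, a range that includes 1d(1) and 1d(2), it says that "sample sizes need not be planned to demonstrate significant differences in these variables".
- **Statistical Analysis and Modeling (III.J.3), item 2** compares the arms "using chi-squares to cross-tabulate categorical variables".
- **III.J.3, item 4** makes the principal result 1a(1) plus favourable tolerability findings. The go sentence is that a significant 1a(1) and "absence of statistically significant differences on 1d(1)-1d(2) will support development of a Phase III clinical trial". The same item adds "We did not hypothesize equal tolerability for rizatriptan and placebo", says that the hypothesis was instead "an absence of significantly higher rates of serious adverse effects and drug-related treatment discontinuation", and on that ground omits equivalence tests. It analyses subjects who treat at least one attack.

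**The concern.** A test that was never sized to find a difference is used so that finding none counts in the drug's favour. The smaller the trial, and the fewer subjects who treat an attack, the easier that criterion is to meet. Hypothesis 1d speaks about rates, whereas item 4 puts in its place a statement about a p-value. If 1a(1) were significant, the plan as written would treat the tolerability part of the principal result as favourable while the data remained compatible with a material excess on rizatriptan.

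Two wording faults sit beside this. The go sentence speaks of differences in either direction, although item 4 says its hypothesis concerned higher rates. And 1d(2) covers adverse events of every kind under III. Approach, but only drug-related discontinuation in item 4.

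**Working it through.** **Inputs from the plan.** 120 subjects at 2:1 gives 80 and 40. This is a ceiling, because only subjects who treat an attack are analysed. The tests are two-sided at 0.05. The plan names chi-square without saying whether it is corrected; I use the uncorrected Pearson form and show Fisher's exact test beside it. The plan gives no expected placebo rate for either measure, so all true event rates below are assumptions.

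**1. The plan's own figure (1a(1)).** With placebo 22% and odds ratio 3.2:
- Rizatriptan odds = 3.2 × 0.22/0.78 = 0.903, so the rate is 0.903/1.903 = 47.4%.
- Pooled rate = (80 × 0.474 + 40 × 0.22)/120 = 0.390.
- SE under the null = √[0.390 × 0.610 × (1/80 + 1/40)] = 0.0944.
- SE under the alternative = √[0.474 × 0.526/80 + 0.22 × 0.78/40] = 0.0861.
- z = (0.254 − 1.96 × 0.0944)/0.0861 = 0.81, so power is 79%.

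This agrees with the stated 80%. The plan has no corresponding figure for 1d.

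**2. What passes the 1d criterion.** z = difference / √[p(1−p)(1/80 + 1/40)], where p is the pooled rate.
- 7/80 against 0/40: p = 7/120 = 0.0583, SE = √(0.0583 × 0.9417 × 0.0375) = 0.0454, z = 0.0875/0.0454 = 1.93. Chi-square p = 0.054, so it passes.
- 8/80 against 0/40: p = 0.0667, SE = 0.0483, z = 2.07. Chi-square p = 0.038, so it fails; Fisher p = 0.051 would still pass.
- With one placebo event, chi-square first flags an excess at 12/80 (p = 0.038).

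The passing 7/80 against 0/40 is an observed excess of 8.8 points. Its exact unconditional 95% interval (two one-sided score tests, maximised over the nuisance rate) is -1.8 to 17.4 points.

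**3. Chance of flagging a true excess on one measure.** Sum of binomial probabilities over all outcomes at 80 and 40 that are significant with the higher rate on rizatriptan:

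| Assumed rizatriptan vs placebo | Chi-square | Fisher |
|---|---|---|
| 5% vs 1% | 3% | 1% |
| 10% vs 2% | 29% | 20% |
| 10% vs 0% | 55% | 41% |
| 20% vs 2% | 88% | 84% |

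The test works for very large excesses and does little for smaller ones.

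**4. Direction.** 0/80 against 2/40: p = 2/120 = 0.0167, SE = √(0.0167 × 0.9833 × 0.0375) = 0.0248, z = −0.05/0.0248 = −2.02. Chi-square p = 0.044 (Fisher 0.109). Read literally, the chi-square result fails the go sentence although it favours rizatriptan.

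**The case against.** The plan is open about its choice: it says these measures are unpowered, disclaims a hypothesis of equal tolerability, and waives equivalence tests for that reason. In the Specific Aims, 1d says only that the drug will be well tolerated. Moving to a further trial when no safety signal has appeared is ordinary Phase II practice. The go sentence itself asserts no comparability, and the oversight board reviews adverse events quarterly (V. Study Oversight).

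Much of this stands, and it limits the weight of the point. It does not remove it. The disclosure shows that the choice was deliberate, but hypothesis 1d in III. Approach still claims tolerability as good as placebo, and item 4 still counts non-significance as favourable.

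The unit of analysis can also be questioned. Serious adverse events are collected after each treated attack, item 4 applies the mixed-model step to these measures too, and a subject-level test is my choice. Counting attacks does not rescue the rule. Even if three attacks per subject (240 against 120) were treated as independent, which is optimistic, the chance of significance at 10% against 5% is about 36% (chi-square) or 33% (Fisher).

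The direction example rests on a very small expected count, 40 × 2/120 = 0.67 placebo events, where chi-square is unreliable. It shows loose wording and adds no weight.

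A reader might infer that the interim analysis (III.J.3, item 7) either cures or repeats the fault. It does neither. It looks for a "statistically significant difference between arms in adverse events of greater than minor severity", which is a different endpoint from 1d.

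**Conclusion.** The point holds as a fault in the decision rule and its wording. At 80 against 40, a non-significant 1d result can leave an excess of up to about 17 points within the 95% interval, and assumed true rates of 5% against 1% would be flagged only about 3% of the time. The detection figures depend on assumed event rates, subject-level counting and the planned maximum sample. The thresholds and the interval depend only on the last two.

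The consequence is confined to the tolerability part of the go statement. Efficacy inference is untouched, and tolerability alone triggers nothing. The results summary at the end of the document reports no difference between arms on the primary outcome, so the go sentence was not met in this trial.

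Three stronger readings are not supported. A reader might infer that rizatriptan is poorly tolerated, but nothing here shows that. A reader might infer that the plan claims to have proved equivalence, but item 4 says otherwise. Or a reader might infer that the trial needed an equivalence test or a larger sample. It did not: it needs only to stop counting non-significance as a favourable finding.

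**What to change.** 1. **Criterion (III.J.3, item 4).** Replace the absence of significant differences with no significantly higher rate on rizatriptan on 1d(1) or 1d(2), so that fewer events on rizatriptan cannot fail the go sentence. Call that outcome *no excess detected*. State that it is neither a favourable finding nor evidence of tolerability comparable to placebo.
2. **Principal result (same item).** Replace the requirement for favourable tolerability findings to match: the go sentence needs a significant 1a(1) and no excess detected on 1d(1) and 1d(2). Beside it, report the rizatriptan-minus-placebo risk difference for each measure, counting each subject once for any event, with exact 95% intervals. Limit any tolerability statement to what the upper limits exclude.
3. **Definitions.** Reword 1d in III. Approach to match. Reconcile the two scopes of 1d(2), adverse events of every kind or drug-related only. State whether withdrawals for serious adverse events count in it; III.H (Safety Procedures) and IV.E.1 (Risk Minimization) describe those withdrawals differently and need to be reconciled.

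The cost is wording and one table, with no extra subjects. The downside is a more modest tolerability claim, because the intervals are wide: even 0/80 against 0/40 gives an exact 95% interval of -9.2 to 5.1 points.

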3. After testing bivariate differences, we will use repeated measures mixed effects models to compare outcome measures between rizatriptan and placebo over time, and examine the effects of covariates on treatment response. As an example, for the special case of binary outcome vertigo severity (Grade 3/2 versus Grade 1/0) and the more general case of ordinal outcome vertigo severity (Grade 3, 2, 1, 0), we will use SAS PROC GLIMMIX to model the logits of cumulative probabilities including vectors for study drug, illness related variables, associated symptoms, rating scales, random effects, and time. The estimates on the linear scale will represent log cumulative odds. The cumulative logits are formed as  $\log \{ \Pr(Y_i \leq j) / \Pr(Y_i > j) \} = X_i \alpha + Z_i \gamma_i + \varepsilon_i$  for  $i=1, \dots, n$ , where  $Y_i$  is the  $n_i \times 1$  vector of the outcome measure for the  $i^{\text{th}}$  patient,  $j=0,1,2,3$ ,  $n_i$  is the number of measurements for the  $i^{\text{th}}$  subject in the period,  $X_i$  is  $n_i \times p$  known predictors (indicator signifying rizatriptan and placebo, and time variable.) The fixed effects parameter vector of  $\alpha$  is  $p \times 1$ .  $Z_i$  is  $n_i \times k$  known predictors, which are associated with the random part of the model, including time-varying and time factors.  $\gamma_i$  is the  $k \times 1$  random effect parameter vector and  $\gamma_i \sim N(0, D)$ ,  $\varepsilon_i$  is  $n_i \times 1$  and  $\varepsilon_i \sim N(0, \sigma^2 I)$ , which is independent of  $\gamma_i$ . Let

$\Sigma_i(\theta) = Z_i D Z_i^T + \sigma^2 I$  with  $\theta$  being the parameter of covariance vector. Integrating out  $\gamma_i$  in the above random effect model, we can write  $Y_i \sim N(X_i \alpha, \Sigma_i(\theta))$ .

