5. Analyses of Specific Aim #2 (a-c) will be descriptive and exploratory. As a Phase II trial, this proposed study is not powered for a thorough examination of covariates and confounds. We will start by reviewing univariate analyses of data collected during the Observation Phase of the study to identify results that will be critical for designing future Phase III trials. First, we will examine the distribution of VM attack frequency and severity (2a) to determine if these variables have normal, skewed, bimodal, or other distributions. This will allow future investigators to estimate recruitment patterns for Phase III studies. Second, we will establish a rank order of comorbid conditions (2b) by prevalence and likelihood of affecting the clinical course or treatment of VM. This will allow future Phase III investigators to understand trade-offs between strictness of subject selection criteria and generalizability of results. Third, we will establish a rank order of usual care and self-medication therapies for VM (2c). This will allow future investigators to establish criteria for allowable co-treatments in Phase III trials. Finally, we will repeat the multivariate modeling of step 3 above, including variables representing data 2a-c collected during the Treatment Phase of the study. Variables found to have significant or trend level effects on rizatriptan versus placebo treatment will mark design considerations for Phase III trials and potentially generate hypotheses for epidemiologic, mechanistic, or other lines of investigation of VM.

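### The Aim 2 covariate model uses attack and medication variables from after randomization, some of which the drug is expected to change, although pre-randomization counterparts are recorded

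*Combined protocol and SAP*

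**What the plan says.** Section III.J.3 item 5 covers Specific Aim 2. It first reviews Observation Phase data univariately, then returns to the drug-versus-placebo mixed model of item 3: "we will repeat the multivariate modeling of step 3 above, including variables representing data 2a-c collected during the Treatment Phase of the study". Its use is stated: "Variables found to have significant or trend level effects on rizatriptan versus placebo treatment will mark design considerations for Phase III trials". Item 5 also sets the status of this work: "Analyses of Specific Aim #2 (a-c) will be descriptive and exploratory", and "this proposed study is not powered for a thorough examination of covariates and confounds".

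Data 2a-c are attack frequency and severity, comorbid conditions, and medication use. Section III (Approach) says of them: "We intend to gather the following specific information during the Observation Phase of this study, which will last up to 12 months". It adds that they are collected again in the Treatment Phase, to explore their influence on rizatriptan's efficacy. Section III.D.2 has attacks, comorbid conditions and all interventions recorded prospectively before randomization at Visit 2.

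The item 3 model is described as containing study drug together with "illness related variables, associated symptoms, rating scales, random effects, and time". No measurement time is given for these covariates. Neither item 3 nor item 5 writes out a treatment-by-covariate interaction.

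**The concern.** Randomization balances what is true of subjects before treatment. Once a covariate has been changed by the assigned drug, subjects with the same covariate value in the two arms are no longer alike, and the adjusted drug coefficient is not the effect of assignment. The same holds for a test of modification: strata defined by a drug-affected variable are not randomized strata.

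The plan itself names some of these variables as drug effects. Hypothesis 1a expects less severe attacks under rizatriptan, and 1a(4) expects fewer non-study therapies. At stake is which variables are carried forward as design considerations for Phase III. A future trial can also select or stratify only on what is known before treatment, so pre-randomization values are the more useful ones.

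**Working it through.** **The plan's own figure.** The plan gives no figure for this analysis. Its only sample-size figure, a detectable odds ratio (OR) of 3.2 with 120 subjects at 2:1, reproduces: placebo 2/9 and OR 3.2 give 47.8% on rizatriptan, and 80 versus 40 subjects give 79.2% power (two-sided 0.05, pooled variance). It is used below only to set the trial size.

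**The passages side by side**

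| Variable in 2a-c | Before randomization | Treatment Phase value open to drug effect? |
|---|---|---|
| Attack severity | Diary, III.D.2 | Yes after dosing (1a); not before the first dose |
| Non-study medication use | Diary, III.D.2 | Yes (1a(4)); allowed from 1 hour post-dose, III.D.4 |
| Prophylactic and comorbidity medication | Stabilized, III.G | No; doses held constant, III.G |
| Attack frequency, comorbidity | III.D.2 | Only if the drug alters them; no passage says so |

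**Algebra.** Let M0 be the value the covariate would take without drug, T the drug indicator, and M = M0 − d·T the Treatment Phase value. If logit P(response) = a + b·T + c·M0, substituting M0 = M + d·T gives a + (b + c·d)·T + c·M. Adjusting for M shifts the drug log OR by c·d. The shift is zero when d = 0, and its sign depends on c and d.

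**Simulation at trial size.** The inputs are assumptions: 80 and 40 subjects; true drug OR 1.00; 2,000 runs per setting; covariate and response share a latent severity (correlation 0.6 with log OR 0.7 per SD, or 0.8 with 1.0); the drug lowers the Treatment Phase covariate by d SD.

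| d | Treatment Phase covariate: median OR | type I error | Pre-randomization covariate: median OR | type I error |
|---|---|---|---|---|
| 0 | 1.00 to 1.01 | 4.6% to 4.8% | 0.99 to 1.01 | 4.1% to 4.6% |
| 0.5 | 0.82 to 0.69 | 7.5% to 12.6% | 1.01 to 1.02 | 5.2% to 5.4% |
| 1.0 | 0.68 to 0.46 | 11.4% to 29.2% | 1.01 | 4.5% to 4.7% |

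The algebra agrees. At d = 1.0, c = ln 0.68 = −0.39 and ln 0.46 = −0.78. Halving d predicts exp(−0.39/2) = 0.82 and exp(−0.78/2) = 0.68, against 0.82 and 0.69 simulated.

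**With a true effect.** Take a true conditional OR of 3.2 (log OR 1.16), latent severity, covariate noise SD 0.5 to 2, and n = 400,000. The pre-randomization covariate gives a log OR of about 1.0 to 1.1. The Treatment Phase covariate gives 0.35 to 0.83 with a drug shift of 1.0, but 0.93 to 0.96 with a shift of 0.25.

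**An example in the other direction.** Take relief at 24 hours judged on the grade alone. (Outcome 1a(2) instead counts relief only without non-study therapies, so rescue use there is part of the outcome's definition.) Assume 40% relief on placebo without rescue, a drug OR of 2.0 at fixed rescue use, and rescue that doubles the odds of relief. Relief with rescue is then 57.1% on placebo and 72.7% on drug; without rescue it is 40% and 57.1%. If 60% of placebo and 40% of rizatriptan attacks are rescued:

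- placebo: 0.6 × 0.571 + 0.4 × 0.400 = 0.503
- rizatriptan: 0.4 × 0.727 + 0.6 × 0.571 = 0.634
- total OR: (0.634/0.366) / (0.503/0.497) = 1.71

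With rescue raising the odds fourfold, the total OR is 1.44. At 70% versus 30% rescued, it is 1.49 (twofold) and 1.11 (fourfold). The rescue-adjusted model reports 2.0 in all four cases, so here adjustment overstates the total effect.

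These calculations address the treatment estimate. Bias in an interaction estimate was argued above but not quantified.

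**The case against.** The case for leaving the text alone is substantial.

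- Item 5 is declared exploratory and unpowered, and the bivariate comparison of item 2 does not depend on it. This stands and limits the consequence. The label lowers the certainty claimed, however; it does not remove bias.
- Other symptomatic medication must wait 1 hour, so rescue in the same attack cannot lie on the path to the 1-hour primary outcome. That is correct. Such rescue can still be a consequence of non-response at 1 hour, and the modeling covers all outcomes, including the 24-hour ones.
- Prophylactic doses are fixed, and one dose per attack for up to three attacks may not alter attack frequency or comorbidity. This also stands: where d = 0 there is no bias.
- At 80 and 40 subjects the standard error of the log OR is about 0.44 (22% placebo response, OR 3.2), comparable to several of the illustrated shifts. True, but a larger sample shrinks the error and not the bias.
- The Observation Phase stops at the second qualifying attack, so the attack count is fixed by design and is no direct substitute. A rate per time observed meets this.

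A reader might infer that Phase III selection criteria and permitted co-treatments would be taken from the biased model. Item 5 ties those to descriptive rankings of comorbidities and therapies; the refitted model only flags design considerations and hypotheses. A reader might also infer that item 3 adjusts for post-dose outcomes. Its text gives no timing, and DHI, GAD-7, PHQ-9 and SF-12 are all collected at Visits 1 and 2 (Table 2), so item 3 needs clarification and is not a demonstrated error.

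**Conclusion.** The concern holds in a limited form. Item 5 expressly puts Treatment Phase 2a-c variables into the rizatriptan-versus-placebo model, the plan's own hypotheses make some of them drug effects, and the plan also records pre-randomization counterparts. The resulting treatment and modifier estimates can be biased.

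The documents fix neither size nor direction. In the illustrations a null effect appears as an OR between 0.82 and 0.46 when the drug lowers the covariate by 0.5 to 1.0 SD, a 0.25 shift does little, and the rescue example errs upward (2.0 against 1.11 to 1.71). A reader might infer error in one predictable direction; these results do not support that. Nor is every Treatment Phase variable suspect: the concern is for post-dose severity and non-study medication use, and for others only if the drug moves them. The randomized bivariate comparison and the sample size are unaffected.

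**What to change.** In item 5, define the candidate modifiers from Observation Phase or Visit 2 values: attack frequency as a rate per time observed, attack severity, comorbidities, medication use, and DHI, GAD-7, PHQ-9 and SF-12. Test each by a treatment-by-variable interaction. Report Treatment Phase 2a-c values by arm, or in an analysis labelled as non-causal.

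In item 3, state that covariates are limited to pre-randomization values plus the pre-dose grade of the treated attack, noting that this grade is strictly pre-treatment only for the first attack.

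The cost is SAP wording; the data are already planned, and sample size and endpoints do not change. The downside is that Observation Phase values may be less current for attacks treated long after randomization, since section IV.B allows a Treatment Phase of up to 4 years.
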